6.9 CONCOMITANT MEDICATIONS

Concomitant medications at baseline and throughout the study period will be described by third dose allocation and priming vaccine stratum. New medications taken during the trial in response to a local or general reaction or an AE will also be recorded. For AEs, the medication taken will be included in a line list of all AEs.

6.10 RESCUE VACCINATION

The protocol specifies that if responses are considered by the DSMB to be inadequate an appropriate rescue strategy will be developed, probably involving a single dose [dosage not specified] of the vaccine in question at 3 months. Rescue vaccination will only be given to participants in the fractional dose groups and will be treated as an intercurrent event using the Treatment Policy strategy, such that the estimand will be a comparison of a standard dose without rescue vaccination vs. a fractional dose with rescue vaccination

^{*}Reasons will be provided.

[^]The number of participants with missing data will be noted (data will be imputed in a sensitivity analysis if missingness is >5%). Missing data arising from lost-to-follow-up or withdrawal will be enumerated, including the level of withdrawal (from intervention, follow-up, or both, and consent to use data up to the time of withdrawal) and reasons (harms-related reasons for withdrawal will be emphasised).

if required for all Month-6 and Month-12 endpoints. Results should be interpreted within the context of the proportion of fractional dose recipients who receive rescue vaccination.

6.11 DEFINITIONS RELATED TO ESTIMANDS

Sections 6.13 'Analysis of the primary endpoints' and 6.14 'Analysis of secondary endpoints' specify analytical approaches for the primary and secondary endpoints using the estimand framework. An estimand is a precise description of the quantity that is estimated to assess the treatment effect reflecting the clinical question posed by a given clinical trial objective. It has 5 attributes: population, treatment, variable of interest e.g., outcome & timepoint, summary measure, and possible intercurrent events (defined as an event that can occur post-randomisation and preclude or affect the interpretation of the variable of interest e.g. discontinuation of treatment). Intercurrent events specific to this trial are described in Section 4.4 'Intercurrent events'.

When defining an estimand, it must be made clear how intercurrent events will be handled in the analysis. Different approaches can be taken towards handling intercurrent events and are described below:

- Hypothetical: a strategy which envisages a scenario in which the intercurrent event would not occur, e.g., if participants had not switched treatment or if death had not occurred
- ii) Treatment policy: a strategy which seeks to understand the treatment effect on the variable regardless of the intercurrent event, i.e., an outcome is of interest whether or not the intercurrent event occurred prior to the outcome, e.g. the final outcome is of interest irrespective of whether the participant takes additional medication
- iii) Composite: a strategy which considers the occurrence of the intercurrent event as informative about the participants outcome. Under this strategy the intercurrent event is included in the endpoint definition, e.g., classifying the use of rescue medication as failure, in addition to disease progression, in a time-to-event analysis
- iv) Principal Stratification: a strategy wherein treatment effects are assessed in the stratum of participants who would have a specific status with respect to the intercurrent event e.g., examining the effect of treatment in participants who would not require rescue medication
- v) While-on-treatment: a strategy which considers response to treatment prior to the occurrence of the intercurrent event to be of interest. For repeated measures, values up to the intercurrent event are of interest but not values after the intercurrent event. Generally, this strategy is only useful if the duration of treatment is not relevant either because it is not clinically relevant or because the rate of an event or outcome is constant over time e.g. the rate of adverse events, where one assumes a constant hazard.

In general, we have leant towards strategies that do not require strong model assumptions (e.g. treatment policy), especially for intercurrent events that are likely to be rare (e.g. breakthrough infections prior to the Day-28 visit). We have specified supplementary analyses that target arguably more relevant estimands that require stronger model assumptions.

Withdrawals/lost-to-follow-up and deaths will be considered as missing data rather than intercurrent events, and will be handled using multiple imputation.⁴

6.12 ESTIMAND-TO-ANALYSIS TABLES

To incorporate the estimand framework into the SAP we use "estimand-to-analysis" tables, as described by Kang, et al. 2022:

"The estimand-to-analysis table template starts with the study objective describing the clinical question of interest as written in the trial protocol. The remainder of the table describes each attribute of the estimand (treatment, target population, variable, intercurrent events, and population-level summary) in the left column (ESTIMAND), while the right column describes how each attribute will be handled using the data collected in the clinical trial (ANALYSIS)."

6.13 ANALYSIS OF THE PRIMARY ENDPOINTS

Table 10. Estimand-to-Analysis table⁵ for seroresponse at Day-28 (primary immunogenicity endpoint)

Primary Objective (as pe	er Protocol): Assess and compare the	e immune response measured as binding antibodies (IgG)	
following standard versu	s fractional doses of either trial vacc	ine given as a single additional dose to adults 18 years or	
older in Indonesia/Mong	olia who have been primed through	previous vaccination with either of the included primary	
series. (Timepoint – 28 d	lays post vaccination)		
Estimand (for each trial vaccine):		The difference in seroresponse proportions 28 days after boosting with a single fractional dose compared to a single standard dose of either of the COVID-19 trial vaccines in adults 18 years or older in [Indonesia/Mongolia] who have been primed through previous vaccination with either of the included primary series, irrespective of SARS-CoV-2 infection.	
ESTIMAND Attributes:		Incorporation of Estimand Attribute in ANALYSIS:	
Treatment Fractional dose (for each	trial vaccine)	Study arms Interventions (for each trial vaccine): Fractional dose	
Target population		Comparisons (for each trial vaccine): Standard dose Analysis set ("Primary Day-28 Immunology	
	in Indonesia/Mongolia who have	Population")	
	evious vaccination with one of the	All randomised participants as per randomisation with	
included primary series.		complete outcome and covariate data	
Variable		Outcome measure	
Seroresponse in binding	antibodies 28 days after boosting.	Seroresponse in binding antibodies at the Day-28 visit	
		(28 – 35 days post-booster), defined as per Table 5.	
Handling of intercurrent	events	Handling of missing data	
Event (up to and	Strategy ^A	The proportion of participants excluded due to missing	
including Day-28 visit)		outcome or covariate data will be described by study	
		group.	
	Treatment Policy (interpret	If >5% of participants are excluded due to missing data,	
SARS-CoV-2 infection	results in conjunction with	a supplementary analysis will be performed with	
	breakthrough infection rates)	multiple imputation (Table 14).	
		marapie impatation (vasie 2 i).	
Population-level summa	ary measure	Analysis approach	
Difference in serorespon	se proportions	The difference between proportions will be estimated	
		with 95% confidence intervals using binomial	
		regression (identity link), adjusting for stratifying	
		variables (age group and primary series), duration	
		between 1st and 2nd, and 2nd and 3rd doses, study day of	
		blood draw, and binding antibody level at baseline ⁶ : glm [seroresponse] [arm] [age group] [primary	
		series] [days 1st-2nd dose] [days 2nd-3rd dose]	
		[study day of blood draw] [baseline antibody], family(binomial) link(identity)	
		Results will be interpreted as described in Section 2.3	
		Framework.	

[&]quot;Supplementary analyses will be conducted using the Hypothetical Strategy for handling intercurrent events (see Table 14).

Table 11. Estimand-to-Analysis⁵ table for at least one solicited grade 3 or 4 local or systemic reaction within 7 days of boosting (primary reactogenicity endpoint)

Primary Objective (as per Protocol): Assess the rate and severity of reactogenicity within one-week post-booster f			
	daily, for seven days post vacci		
Estimand:		Incidence risk of a grade 3 or 4 local or systemic reaction within 7 days (inclusive) of boosting, by dosage (fractional or standard) and trial vaccine in adults 18 years or older in [Indonesia/Mongolia] who have been primed through previous vaccination with either of the included primary series.	
ESTIMAND Attributes:		Incorporation of Estimand Attribute in ANALYSIS:	
Treatment Fractional dose (for each	trial vaccine)	Study arms Interventions (for each trial vaccine): Fractional dose Comparisons (for each trial vaccine): Standard dose	
Target population Adults 18 years or older in Indonesia/Mongolia who have been primed through previous vaccination with one of the included primary series.		Analysis set ("Reactogenicity Population") All participants, as per trial vaccine received (regardless of allocation).	
Variable Grade 3 or 4 local or systemic reaction within 7 days (inclusive) of boosting.		Outcome measure Presence of at least one solicited grade 3 or 4 local or systemic reaction within 7 days (inclusive) of boosting.	
Handling of intercurrent	events	Handling of missing data	
Event (up to and including Day-7) SARS-CoV-2 infection Death	Strategy ^A While Negative (values up to the day of the first positive test are used) While Alive (values up to the time of death are used)	It will be assumed that participants with missing reactogenicity datapoints (collected daily for each reaction type) did not experience the specific reaction on the day/s where the value is missing. Missing data by day and reaction will be described by study group.	
Population-level summa	ry measure	Analysis approach	
Incidence risk (proportion	n) of at least one solicited emic reaction within 7 days	Proportions will be estimated with 95% Clopper-Pearson binomial confidence intervals using the Ci Stata command.	
		Supplementary analysis: The following reaction-specific descriptive analyses will also be conducted: Number and percentage of individuals with each reaction type, presented in a radial graph (Dummy Figure 3). Number and percentage of participants with each reaction type, by severity grade (Dummy Figure S 3). Distribution of the day of onset for each reaction type Distribution of the duration of each reaction type	

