11.2 Population to be analysed

Analysis of this trial is planned on both the intention-to-treat population (ITT), with all participants to be analysed in the group they were randomised to, as well as on the per-protocol (PP) population, consisting of participants who adhered to the study protocol. However, it is expected that withdrawn participants may not have data to contribute at all time points as blood samples may not be collected after the time of their withdrawal.

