1.1 GENERIC TERMINOLOGY

The country-specific studies differ primarily in the trial vaccines being studied and the primary series strata, determined by which booster vaccines are available and which priming vaccines were most used in each country. For text that is relevant to all countries, generic terminology will be used:

- "Trial vaccines" refers to:
 - Indonesia Trial: Pfizer (Comirnaty®), Moderna (Spikevax®), or AstraZeneca (Vaxzevria®)
 - BCOV22 (and BCOV21): Pfizer (Comirnaty®) or AstraZeneca (Vaxzevria®)
 - o Mongolia Trial: Pfizer (Comirnaty®) only
- · "Included primary series" refers to:
 - Indonesia Trial and BCOV22 (and BCOV21): Two doses of either Sinovac (CoronaVac*) or AstraZeneca (Vaxzevria*)
 - Mongolia Trial: Two doses of either Sinopharm (Covilo®), AstraZeneca (Vaxzevria®), or Gamaleya (Sputnik®) vaccines

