6 STATISTICAL METHODOLOGY

6.1 GENERAL METHODOLOGY

6.1.1 Summary of changes compared to the protocols

- "Functional antibodies" have been described more precisely as "ACE2 binding inhibition by neutralising antibody" in the SAP.
- The SAP added to the definition of seroresponse a specification for participants with binding antibody levels under the limit of detection.
- The "interim analysis" described in the protocol is considered in the SAP as the final
 analysis of the Day-28 endpoints as the intention is to only conduct this analysis
 once all Day-28 data is available (no interim analyses are specified in the SAP).
- Grading for hardness and swelling in Mongolia will not consider interference with daily activities as per the protocol as this information is not being captured.
- The protocol does not specify blinding/unblinding of statisticians and data analysts (only specified for participants, those evaluating reactogenicity, vaccinator, immunologists and laboratory staff, clinical investigators); details on blinding of statisticians and data analysts are specified in this SAP.
- In the Mongolia trial protocol, warmth and itch are binary presence/absence variables, with presence falling under Grade 3 and 4 reactions; in the SAP, warmth and itch are to be analysed as binary presence/absence variables with no grading.
- The BCOV22 protocol specifies non-inferiority analyses in terms of seroresponse at Day-28 (from BCOV21), Month-6, and Month-12. The analysis of Day-28 binding antibody data from BCOV21 has already been conducted by the BCOV21 investigators, and this SAP does not specify re-analysis of this data. Further, Month-6 and Month-12 analyses specified in this SAP are based on the superiority framework and will use continuous data only (a binary seroresponse variable will not be considered).

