6.6 PARTICIPANT DISPOSITION

A CONSORT flow diagram will be used to summarise the study population from screening to analysis, including the number of people who were:

- Screened for eligibility
 - o and were eligible at screening
 - and were ineligible at screening (screen failures)*
- Eligible at screening but not randomised*
- Ineligible at screening but randomised (protocol violation)*
- Eligible and randomised

[Subsequent numbers will be given by study group]

- · Allocated to each study group
 - o and received the allocated vaccine
 - and did not receive the allocated vaccine*
- Included in the Reactogenicity and Safety Population (according to vaccine received not allocated)^{*}
- Included in the Primary Day-28 Immunology Population^{*}
- Included in the Secondary Day-28 Immunology Population^{*}
- Included in the Month-6 Immunology Population[^]

Included in the Month-12 Immunology Population^{*}

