6.8 ADHERENCE AND PROTOCOL DEVIATIONS

Adherence to the intervention is defined as receiving a trial booster vaccination on Day 0. The number and percent of participants who adhered will be presented by study group.

Pre-defined major protocol deviations (with a direct bearing on the primary outcome) are:

- Receiving a 4th dose prior to the Day-28 visit
- Inclusion and randomisation of an ineligible person
- Receiving the wrong trial vaccination
- Day-28 visit occurring outside of the specified time window (between Day 28 and 35 [inclusive], with Day 0 being the day of trial vaccination)

All protocol deviations will be classified as minor or major prior to unblinding. Major protocol deviations are those that are deemed to significantly affect the rights or safety of a trial participant, or the reliability, accuracy, and robustness of the data. The number and percentage of patients with major and minor protocol deviations will be summarised by study group (as per randomisation), with details of type of deviation provided.

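### The protocol plans a per-protocol analysis, but the SAP has none for the primary non-inferiority endpoint, so the effect of major deviations on the verdict is never tested

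*SAP*

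**What the plan says.** Protocol 11.2 plans to analyse participants as randomised, "as well as on the per-protocol (PP) population, consisting of participants who adhered to the study protocol".

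For primary endpoint (i), SAP Table 10 (section 6.13) gives a single set, the Primary Day-28 Immunology Population: "All randomised participants as per randomisation with" complete outcome and covariate data. The participant flow in 6.6, the supplementary and sensitivity analyses in Table 14 and the planned outputs in section 7 contain no per-protocol set. SAP 6.1.1, "Summary of changes compared to the protocols", has no entry on it, although it lists changes as minor as the grading of warmth and itch.

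The SAP does report deviations. Section 6.6 counts by study group, with reasons, those who were allocated "and did not receive the allocated vaccine". Section 6.8 opens a list with "Pre-defined major protocol deviations (with a direct bearing on the primary outcome) are" and names four: a 4th dose before the Day-28 visit, randomisation of an ineligible person, "Receiving the wrong trial vaccination", and a Day-28 visit outside Days 28 to 35. These are to be classified before unblinding and summarised by arm. SAP 1.1 lists the trial vaccines as "Mongolia Trial: Pfizer (Comirnaty®) only".

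**The concern.** In a non-inferiority comparison, errors that make the arms more alike work in favour of success. A participant who receives the other arm's dose does this directly if the doses differ in effect. For ineligible or out-of-window participants, the direction and size of any effect are uncertain.

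Counting deviations shows how many occurred. It does not show whether the lower confidence limit stays above -10% without them. A comparative re-analysis also cannot simply be added at the reporting stage, because SAP 6.1.8 permits extra descriptive statistics but not extra comparative ones.

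A second gap is in the definitions. With only one trial vaccine in Mongolia, it is unclear whether the third deviation in 6.8 covers receipt of the unallocated dose. The adherence definition in the same section asks only for a trial booster on Day 0, so someone given the wrong dose would count as adherent.

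**Working it through.** **1. What each planned analysis does with the four deviations (primary endpoint (i))**

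| Deviation in SAP 6.8 | Handling in Table 10 or Table 14 |
|---|---|
| 4th dose before Day-28 visit | None. SAP 4.4 calls a 4th dose an intercurrent event and refers to the later tables for a strategy, but Table 10 gives one for SARS-CoV-2 infection only |
| Ineligible but randomised | None |
| Wrong vaccination | None |
| Visit outside Days 28-35 | Partial: the outcome is defined at 28-35 days, and blood-draw day is a covariate ("study day of blood draw] [baseline antibody], family(binomial) link(identity") |

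For this endpoint, Table 14's supplementary analysis changes only how infections are handled, and its sensitivity analysis addresses only missing data.

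**2. Reproducing the plan's power figures**

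Inputs from protocol 11.1 and 11.3: 95% seroresponse in both arms, margin -10 points, lower limit of a two-sided 95% interval.

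Power = Φ[(0.10 - (p_S - p_F))/SE - 1.96], with SE = √[p_S(1-p_S)/n + p_F(1-p_F)/n].

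- n = 100: SE = √(0.095/100) = 0.0308, power 90.05%.
- n = 200: SE = √(0.095/200) = 0.0218, power 99.57%.

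These match the stated 90% and >99%.

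**3. Dose crossover at the margin**

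Assumptions: true rates are 95% (standard) and 85% (fractional), and a share x of each arm receives the other dose. Then

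- p_S = 0.95(1-x) + 0.85x
- p_F = 0.85(1-x) + 0.95x
- p_F - p_S = -0.10(1-2x)

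Example with x = 2%, n = 400: p_S = 0.948, p_F = 0.852, difference -0.096, SE = √[(0.948×0.052 + 0.852×0.148)/400] = 0.0209. P(lower limit > -0.10) = Φ(0.004/0.0209 - 1.96) = 3.85%.

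The probability of falsely declaring non-inferiority is shown below as normal approximation / exact enumeration. The enumeration sums binomial probabilities over all outcome pairs whose Newcombe score lower limit exceeds -0.10.

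| x | Difference | n = 100 | n = 200 | n = 400 |
|---|---|---|---|---|
| 0 | -10.0 | 2.50 / 2.31% | 2.50 / 2.53% | 2.50 / 2.57% |
| 1% | -9.8 | 2.79 / 2.58% | 2.92 / 2.95% | 3.11 / 3.19% |
| 2% | -9.6 | 3.11 / 2.87% | 3.40 / 3.42% | 3.85 / 3.93% |
| 5% | -9.0 | 4.26 / 3.92% | 5.23 / 5.21% | 6.90 / 6.98% |
| 10% | -8.0 | 6.89 / 6.32% | 9.90 / 9.71% | 15.66 / 15.59% |

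If only the fractional arm is affected, the normal approximation for n = 100, 200 and 400 gives 2.64, 2.70 and 2.79% at x = 1%, and 2.79, 2.92 and 3.12% at x = 2%. One to two per cent of an arm of 400 is 4 to 8 people.

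**4. Power of an added per-protocol analysis (95% in both arms)**

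| Planned n per group | Excluded | n left | Normal approximation | Newcombe, exact |
|---|---|---|---|---|
| 100 | 0 | 100 | 90.05% | 83.2% |
| 100 | 5% | 95 | 88.5% | 81.4% |
| 100 | 10% | 90 | 86.8% | 79.4% |
| 200 | 0 | 200 | 99.57% | 98.9% |
| 200 | 10% | 180 | 99.16% | 98.2% |

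At 400 per arm, power stays above 99.9% on either method with up to 10% excluded.

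**The case against.** The SAP was written against protocol 81800 V4, with 12-month follow-up, whereas the supplied protocol runs to 24 months. If V4 had no per-protocol plan, 6.1.1 had nothing to declare. This stands as a limit: the finding is that the two supplied documents disagree, not that the SAP's authors knowingly dropped an analysis.

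The as-randomised choice also looks deliberate. SAP 6.11 adopts the estimand framework and leans towards strategies with weak model assumptions, and a per-protocol subset removes people on post-randomisation events. That is a fair reason to keep the as-randomised analysis primary. It does not explain the conflict with protocol 11.2, and Table 10 gives no strategy for these deviations.

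The effect is probably small. Vaccinators read the dose from REDCap, dose modification is not permitted, and eligibility and primary-outcome data are fully monitored. Rescue doses are foreseen at about 3 months or after DSMB review, so few 4th doses should precede the Day-28 visit. If the doses do not differ, crossover causes no shrinkage. All of this stands and limits the weight of the point.

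The ambiguity over the wrong vaccination may be only one of wording: SAP Table 1 lists the two doses as separate study groups, so dose is probably meant. One clarifying sentence would settle it.

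Finally, power under the score interval named in protocol 11.3 is lower than under the normal approximation (section 4 of the working). That is correct, and a discordant result in a group of 100 could reflect lost precision alone. It argues for a supportive role, not for omission.

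**Conclusion.** The concern holds. The supplied protocol plans a per-protocol analysis that the SAP does not contain, and the SAP neither declares nor justifies the difference. Three of the four major deviations it names have no planned analysis for the primary endpoint, and the fourth is only partly handled.

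The likely bias is modest. With 1-2% of each arm given the other dose and a true difference exactly at the margin, false non-inferiority rises from a nominal 2.5% to about 2.6-3.9%. It becomes material only at swap rates of 5-10%. These rates are assumptions, since the documents give none, and only dose crossover has been quantified. The case rests mainly on the undeclared departure for the trial's main claim. The change should be made, but the primary analysis does not depend on it.

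**What to change.** - In SAP 6.13 and Table 14, add a supplementary per-protocol analysis of primary endpoint (i): the Primary Day-28 Immunology Population without participants who have any of the four deviations in 6.8, classified before unblinding as 6.8 already requires. Say whether other deviations classed as major are also excluded.
- State that, for Mongolia, the wrong-vaccination item includes receiving the dose not allocated.
- Use the same model and the same -10% margin. Show the per-protocol count in the CONSORT diagram, and the result beside the as-randomised one in Figures 2 and S1.
- Keep the success criterion in 2.3 on the as-randomised analysis. Report any discordance and discuss it when non-inferiority is interpreted.
- Record the relation to protocol 11.2 in 6.1.1.

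If the code has already been run with real allocations, SAP 3.5 provides for revisions by staff without access to those data.

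The cost is one further run of an existing model on data already collected, plus wording. The per-protocol set is smaller and no longer strictly randomised, and its power in the groups of 100 is a few points lower. Because it has no veto, the main analysis loses no power.
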